7.1 Inclusion Criteria

- Male or female of any race ≥ 18 years ≤ 80 years of age.
- Diagnosis of intractable glaucoma in the study eye, with the exception of silicone oil endotamponade induced glaucoma, which has not responded to conventional medical and surgical therapy.
- Elevated intraocular pressure > 21 mmHg in the study eye. Two consecutive measurements using Goldmann Applanation Tonometry will be obtained and the mean of those two measurements will be considered the subject's baseline intraocular pressure.
- Subject is a candidate for surgery in the study eye with a glaucoma drainage device.
- Subject is willing and able to sign the informed consent.

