9.4 Device Explant, Repositioning, or Replacement

The device may be revised, repositioned, removed, or replaced by the same kind of device or another marked drainage device if the original device was damaged or determined to be not functioning. If surgical intervention for repositioning or replacement is required, the subject will be required at a minimum to complete all of the protocol required post-operative visits. If sequelae persist, the subject should be followed until all sequelae are considered to be stabilized or resolved.

10. Safety

At each visit, the ocular health of the subject will be assessed. The cornea, anterior chamber, trabecular meshwork, device implant location (if available), and fundus will be examined. Any ocular unanticipated adverse events occurring during the study whether they are considered to be device related or not, must be documented on the Adverse Event Case Report Form. Date and time of the event, event severity, treatment (if any), and the assessed relationship of the event to the study devices will be recorded on the Adverse Event Case Report Form. Conditions that exist at the time the subject is enrolled in the study do not need to be recorded on the Adverse Event Form as adverse events, unless they increase in severity during the study and constitute an unanticipated adverse event..

The collection and recording of unanticipated adverse events will begin at the start of the surgical intervention and will end at the subject's Month 12 or Early Termination Visit. Unanticipated adverse events must be followed until the adverse event has recovered or recovered with ongoing sequelae that will likely not change in the view of the investigator. This period *may* extend beyond study termination.

A brief overview of the differences between anticipated, unanticipated and serious adverse events is provided.

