10.1 Anticipated Adverse Events

Anticipated adverse events include those that might reasonably be expected to occur in this study because they are associated with glaucoma surgical procedures. Anticipated adverse events for both the porous plate and silicone plate glaucoma valves include:

- * Wound Leak
- * Shallow Anterior Chamber

- * Flat Anterior Chamber
- * Choroidal effusion
- * Exposure of Tube, Patch Graft, Plate
- * Severe Inflammation
- * Tube and/or Flow Obstruction
- * Corneal Edema
- * Motility Disturbance (i.e. Diplopia)
- * Suprachoroidal hemorrhage
- * Hypotony (≤ 5 mmHg)
- * Elevated intraocular pressure
- * Retinal Detachment

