10.2 Unanticipated Adverse Events

Unanticipated adverse events include any serious adverse effects on health or safety or any life-threatening problem or death caused by or likely directly related to the Ahmed Glaucoma Valve (M4 or FP7) or the placement of the Ahmed Glaucoma Valve (M4 or FP7) within the eye that are not typically associated with glaucoma surgical procedures.

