11.3 Assessment of the Secondary Endpoints

This secondary endpoint is the mean number of anti-glaucoma medications and surgical success in the porous plate group as compared to the silicone plate group at 12 months. The baseline number of medications will be compared to check for statistically significant differences and, if needed, a change from baseline analysis will be performed. The statistical significance of the differences in the number of medications will be determined using two-tailed paired t-tests. The mean number of medications at individual time points will be compared in the two groups. Kaplan-Meier survival analysis will be performed for statistical analysis of success rates, with comparisons of groups using the log rank test. Complications will be compared using comparison of proportions (z) test.

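### Non-serious worsening of a listed complication present at enrolment never requires the Adverse Event Form or a severity grade, as part of a wider gap covering all non-serious anticipated complications

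*Combined protocol and SAP*

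**What the plan says.** The opening text of Section 10 sets the scope of the Adverse Event Form: "Any ocular unanticipated adverse events occurring during the study whether they are considered to be device related or not, must be documented". Conditions present at enrolment "do not need to be recorded on the Adverse Event Form as adverse events". The exemption is lifted by a single clause with two parts, joined by a conjunction: "unless they increase in severity during the study and constitute an unanticipated adverse event".

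The two classes of event are defined by opposite properties. In 10.1: "Anticipated adverse events include those that might reasonably be expected to occur in this study because they are associated with glaucoma surgical procedures". A list of 13 entries follows, introduced by "Anticipated adverse events for both the porous plate and silicone plate glaucoma valves include". In 10.2, unanticipated events are serious or life-threatening effects, or death, tied to the valve or its placement, "that are not typically associated with glaucoma surgical procedures".

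Section 10.4 asks for a severity assessment of unanticipated and serious events only. Section 10.5 again ties the Adverse Event Form to unanticipated events. It gives serious events a separate form and a 24-hour report to the Medical Monitor. It also makes the investigator responsible for collecting information on both classes, and sends all adverse events to the Institutional Review Board under each site's guidelines.

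For the analysis, 11.3 states: "Complications will be compared using comparison of proportions (z) test". Section 11.6 tabulates adverse events by type and severity.

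**The concern.** A rule on pre-existing conditions normally separates what the patient brought to the trial from what happened in it, and worsening is the usual dividing line. Here worsening alone is not enough: the event must also be unanticipated. For a condition on the protocol's own list of expected complications, that second test fails however far the eye deteriorates, unless the event becomes serious.

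The population makes this more than a technicality. Eyes have failed medical and surgical therapy, and 7.2 admits prior ocular surgery (other than a drainage implant) and conjunctival scarring. Some may therefore enter with corneal edema, inflammation, a shallow chamber or a motility disturbance. The introduction says that the porous plate has not been studied in clinical trials, so the comparison of complications is where the trial would show a disadvantage of that plate. If the input to that comparison is optional, under-recording is possible, and it need not be equal in the two arms of an unmasked study.

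**Working it through.** No formula applies, and the plan gives no figure to reproduce. The check is to follow each kind of event through the recording rules.

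**Step 1: are the two classes exclusive?** In effect, yes. One is defined by association with glaucoma surgery and the other by the absence of a typical association. No clause turns an anticipated event into an unanticipated one because it is unusually severe. Section 10.2 also speaks of serious or life-threatening effects, so non-serious worsening fails it on that ground too.

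**Step 2: what does each kind of event require?**

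| Event in the study eye | Adverse Event Form (10, 10.5) | Severity grade (10.4) |
|---|---|---|
| Listed condition, present at enrolment, worse, not serious | Not required: worsens, but not unanticipated | Not required |
| Listed condition, new, not serious | Not required: not unanticipated | Not required |
| Listed condition, new or worse, meeting 10.3 | Serious Adverse Event form instead | Required |
| Unanticipated event under 10.2 | Required | Required |

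The first two rows end in the same place. The exemption clause adds a second barrier for eyes that started with the condition, but the first barrier already applies to every eye.

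**Step 3: which listed conditions can pre-exist?** Of the 13 entries, three cannot. Hypotony (≤ 5 mmHg) is incompatible with the entry criterion "Elevated intraocular pressure > 21 mmHg in the study eye". Exposure of the tube, graft or plate and tube or flow obstruction presuppose an implant, and 7.2 excludes prior implants. A fourth, elevated intraocular pressure, is present in every eye by that criterion but is measured elsewhere (see the objection). That leaves 13 − 3 − 1 = 9 entries that the eligibility criteria do not rule out at enrolment, though some will be rare then. Corneal edema, severe inflammation, shallow chamber and motility disturbance are the clearest examples.

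**Step 4: do the analyses need what is not required?** Section 11.6 needs a severity for each adverse event, but 10.4 assigns none to the first two rows. Section 11.3 needs a count of complications per arm, but names no source for it and gives no rule for a complication already present at baseline.

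**Step 5: can the under-count be sized?** No. If 11.3 draws on the Adverse Event Form, no eye is required to contribute a non-serious listed complication, whatever its baseline status. If it draws on the assessment of device complications at each visit (8.3), the exemption clause does not govern that item, because it speaks only of the form. Neither route yields a loss confined to eyes with the condition at baseline. The documents give no baseline prevalence and no complication rates.

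**The case against.** The strongest reply is that the clause is narrow. It says what need not go on one form; it does not redefine an adverse event or forbid recording. Other routes remain: the serious-event form whatever the baseline or anticipated status, the duty in 10.5 to collect anticipated events, reporting to review boards, the device-complication item at each visit, and the treatment-failure record in 11.6. The clause also largely repeats a scope that the form already has. A Manual of Procedures, mentioned in 10.5 but not among the documents, may supply a complications form.

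Much of this stands, and it rules out three stronger readings that a reader might infer.

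- *Worsening of a listed condition can never count as an adverse event.* The text does not say so. Serious worsening has its own form, and anticipated events are still to be collected and reported.
- *Eyes with the condition at baseline are selectively lost, so complication rates and power shrink in proportion to their number.* This needs new listed complications to be recorded while worsened ones are dropped. The documents create no such asymmetry.
- *Elevated intraocular pressure is lost in every subject.* Pressure is measured at every post-operative visit, is the primary endpoint, enters surgical success in 5.2, and is documented as treatment failure when raised.

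The other routes still do not close the gap for non-serious edema, inflammation, shallow chamber or diplopia. The collection duty names no form or grade, reporting to review boards follows local guidelines, the visit item has no rule for new versus worse, and the treatment-failure examples do not include these conditions.

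**Conclusion.** The point holds as a defect in the recording rules. Followed as written, the protocol never requires a form or a severity grade for non-serious worsening of a listed condition that was present at enrolment. The same is true of non-serious listed complications that are new. Both kinds are inputs to analyses that 11.3 and 11.6 promise. Recording is left to site discretion in an unmasked trial, so the complication comparison could be incomplete and uneven between sites or arms, in a direction that cannot be foreseen.

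No size can be attached to the under-count. The primary endpoint, the success endpoint and serious-event reporting are not affected. The conclusion assumes that the non-exhaustive definitions in 10.1 and 10.2 are applied in their ordinary sense, and that no manual outside these documents already requires a graded complications form. If one does, the protocol text should be brought into line with it. The correction should be made, because it is cheap and concerns the safety comparison of a plate without prior clinical trial data.

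**What to change.** Change the related sentences together. Altering the exemption clause alone would put worsened anticipated conditions on the form while new ones stayed off it.

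1. **Section 10 (opening text), 10.4 and 10.5:** require recording and severity grading of all ocular adverse events, anticipated or unanticipated, over the collection period already set. Serious events keep their own form and timeline.
2. **Section 10, exemption clause:** end it with *unless they increase in severity from the baseline examination, whether anticipated or unanticipated*.
3. **Section 11.3:** count an eye as having a complication when a 10.1 condition is new or worse than at the 8.1 baseline examination, and name the form that supplies the count. Leave pressure outcomes to the primary and success endpoints.

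The baseline slit-lamp, gonioscopy and funduscopy are already required by 8.1. That section lists no motility examination, so the baseline status for diplopia would have to come from the ocular history or from one added item. The cost is a few sentences of text, somewhat more form completion at the sites, and reported complication rates slightly less favourable in both arms.

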10.1 Anticipated Adverse Events

Anticipated adverse events include those that might reasonably be expected to occur in this study because they are associated with glaucoma surgical procedures. Anticipated adverse events for both the porous plate and silicone plate glaucoma valves include:

- * Wound Leak
- * Shallow Anterior Chamber

- * Flat Anterior Chamber
- * Choroidal effusion
- * Exposure of Tube, Patch Graft, Plate
- * Severe Inflammation
- * Tube and/or Flow Obstruction
- * Corneal Edema
- * Motility Disturbance (i.e. Diplopia)
- * Suprachoroidal hemorrhage
- * Hypotony (≤ 5 mmHg)
- * Elevated intraocular pressure
- * Retinal Detachment

10.2 Unanticipated Adverse Events

Unanticipated adverse events include any serious adverse effects on health or safety or any life-threatening problem or death caused by or likely directly related to the Ahmed Glaucoma Valve (M4 or FP7) or the placement of the Ahmed Glaucoma Valve (M4 or FP7) within the eye that are not typically associated with glaucoma surgical procedures.

10.3 Serious Adverse Events

Serious adverse events include those events that require (≥ 24 hours) or prolong hospitalization, require surgical intervention, are sight or life-threatening or fatal, or result in significant disability or incapacity.

10.4 Assessment of Adverse Event Severity

The investigator will make an assessment of event severity for each unanticipated adverse event and serious adverse event reported during the study according to the following definitions:

Mild: An event that is easily tolerated by the subject, causing minimal discomfort and not interfering with everyday activities.

Moderate: An event that is sufficiently discomforting to interfere with the subject's normal everyday activities.

Severe: An event that prevents the subject's normal everyday activities.

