10.5 Reporting Adverse Events

Identification and collection of anticipated and unanticipated adverse event information is the responsibility of the study investigator. All unanticipated adverse events should be documented by completing the Adverse Event Case Report Form. and submitted to the study coordinating site per study Manual of Procedures. All adverse events (**whether anticipated or unanticipated**) should be reported to the Institutional Review Board according to site guidelines.

The identification and collection of serious adverse events is the responsibility of the study investigator. All serious adverse events should be documented by completion of the Serious Adverse Event Case Report Form. All Serious Adverse events should be reported to the Medical Monitor within 24 hours of the site's notification of the event and to the Institutional Review Board according to site guidelines.

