11.6 Plans for Final Analysis

Subjects will be monitored until they complete the study period. Primary analysis will include all subjects undergoing the study surgical intervention. All subjects who receive any study intervention will be monitored for adverse events. Adverse event information will be tabulated by type and severity of adverse events. If the subject is determined to be a treatment failure (e.g., increased intraocular pressure, hypotony, loss of light perception vision, or additional glaucoma surgery), this will be documented in the study database.

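### The Section 11.6 severity table has no specified data source for non-serious anticipated complications, because severity grading is required only for unanticipated and serious events

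*Combined protocol and SAP*

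**What the plan says.** On data capture:

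- Section 10.4 sets the scope of grading: "The investigator will make an assessment of event severity for each unanticipated adverse event and serious adverse event reported during the study". The scale has three levels, based on discomfort and interference with daily life.
- The opening text of Section 10 requires the Adverse Event form for unanticipated ocular events, whatever their relation to the device, and lists what that form holds: "Date and time of the event, event severity, treatment (if any), and the assessed relationship of the event to the study devices will be recorded".
- Section 10.5 repeats the scope: "All unanticipated adverse events should be documented by completing the Adverse Event Case Report Form". Serious events have their own form: "All serious adverse events should be documented by completion of the Serious Adverse Event Case Report Form".
- Section 10.5 also states that "Identification and collection of anticipated and unanticipated adverse event information is the responsibility of the study investigator". For anticipated events it names no form and no grade. The only reporting route it gives for them is the Institutional Review Board, under site guidelines.
- Section 8.3 requires adverse events and device complications to be reviewed at every post-operative visit. It states no severity item.

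On analysis:

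- Section 11.6: "Adverse event information will be tabulated by type and severity of adverse events".
- Section 11.3: "Complications will be compared using comparison of proportions (z) test".

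**The concern.** The complications expected with either valve, such as wound leak, shallow chamber, choroidal effusion, exposure, corneal edema and diplopia, are all classed as anticipated in Section 10.1. Unless such an event is serious, the grading rule and the form rule both pass it by, while the planned safety table assumes that a severity exists.

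Section 1 notes that the porous plate has not been studied in clinical trials, so its complication profile against silicone is an important safety output. If only presence is recorded, a mild event and one that limits daily activities count alike within the non-serious class. Later repair would be weak: the trial is unmasked, and grades assigned afterwards from charts would be given with the plate known.

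**Working it through.** No arithmetic applies, and the plan gives no figure to reproduce. The check sets the capture rules beside the planned analyses.

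**Step 1. What is required for each class of event**

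| Class | Form named | Severity grade | Date and relationship |
|---|---|---|---|
| Unanticipated (10.2) | Adverse Event form (10, 10.5) | Required (10, 10.4) | Required (10) |
| Serious, including serious anticipated (10.3) | Serious Adverse Event form (10.5) | Required (10.4) | Form content not described |
| Non-serious anticipated (10.1) | None | None specified | None specified |

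**Step 2. How wide the graded classes are.** Section 10.2 describes unanticipated events as serious, life-threatening or fatal effects tied to the valve or its placement and not typical of glaucoma surgery. Section 10.3 covers hospitalization, surgical intervention, threat to sight or life, death, and significant disability. In practice, therefore, grading covers essentially serious events.

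**Step 3. What falls outside.** Section 10.1 lists 13 types, and each is ungraded when non-serious. Two of them, hypotony and elevated intraocular pressure, have a measured magnitude because pressure is taken at every post-operative visit. That leaves 13 − 2 = 11 types without a pressure value to stand in for a grade. One of the 11, suprachoroidal hemorrhage, is named in Section 11.5 as vision-threatening and so should meet 10.3 and be graded.

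**Step 4. What the analyses need.** The z test in 11.3 needs only whether a complication occurred. Occurrence is to be collected by the investigator (10.5) and is assessed at each visit (8.3), although no form is named for it. The table in 11.6 needs a severity for each event and carries no restriction to unanticipated or serious events. For the third row of the table above, the protocol specifies no source for that severity.

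**Step 5. Whether another section fills the gap.** Section 10.6 begins with follow-up of any adverse event, then limits its mandatory follow-up to unanticipated events, and ends by sending follow-up to the Adverse Event form. The last sentence is ambiguous, but it concerns follow-up and creates no duty to grade.

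**The case against.** The strongest reply is that little is lost. The primary endpoint is mean intraocular pressure, the secondary endpoints are medications and surgical success, and Section 5 lists no safety endpoint. The 11.3 comparison needs occurrence only. Complications that need surgery or threaten sight are serious and are graded even when anticipated. Slit lamp, funduscopy and acuity are required at each visit. The capture rules also point to a manual of procedures that is not supplied, and no case report form is available, so a complications page may already have a severity field.

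Much of this stands, and it rules out several stronger readings that a reader might infer:

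- *That the between-arm complication test lacks data.* Not shown; it needs only occurrence.
- *That complications are the core of the plate comparison.* Section 5 says otherwise; they matter to the safety comparison.
- *That most events would go ungraded.* The documents give no complication rates.
- *That a plate with worse complications would look equally safe.* Serious ones are graded, so the blind spot lies within the non-serious class.
- *That the severity column will be empty.* The protocol leaves the source unspecified; what the unseen manual or forms contain cannot be known.

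It is also fair to say that the 10.4 scale, being about daily activities, would not by itself separate trace from marked clinical signs or brief from lasting events.

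What does not stand is that the manual settles the matter. Sections 10.5 and 10.6 cite it for submission and time frames. If it does require grading of anticipated events, it goes beyond 10.4, and the two still need reconciling.

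**Conclusion.** The mismatch is real and confined to one class of event. A site that follows Sections 10, 10.4 and 10.5 exactly need supply no severity, dates or relationship for a non-serious anticipated complication, yet 11.6 plans a severity table that includes such events. This is a restrictive rule that conflicts with a planned analysis, rather than detail left for later.

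The effect falls on the descriptive safety table. The primary and secondary efficacy analyses are untouched. The share of events affected cannot be stated. The conclusion assumes that the protocol text governs what sites record and that no unsupplied manual or form adds a grading requirement. It should be corrected, given how little the change costs.

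**What to change.** Amend Sections 10, 10.4 and 10.5 so that every ocular adverse event in the study eye, anticipated or not, from the start of surgery to month 12 (or early termination, the window Section 10 already uses) is entered on the existing Adverse Event form with onset date, end date, severity grade and relationship. Name this record as the source for both the 11.3 comparison and the 11.6 table. The end date is needed because the 10.4 scale does not capture duration.

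The cost is wording in three places and more form entries at sites, for events already looked for at each visit.

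The minimum alternative is to limit the 11.6 severity table to unanticipated and serious events, tabulate other anticipated events by type only, and state that limit when safety is reported. This removes the contradiction at almost no cost but gives up severity information on non-serious complications.
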